### **6.0 Study Procedures**

**1. Theoretical Framework.** DECIDE is grounded in mental health disparities frameworks and social cognitive principles. The parent component is designed to increase parent activation, to help effectively ask questions and participate in decisions about care. The provider component is designed to teach provider communication skills in listening, eliciting the patient's agenda, encouraging question, and providing management education.

**2. Preliminary Studies.** Drs. [name], [name], [name], and [name] collaborated on the preliminary studies below. For this application, we added [name] (Consultant) who is a nationally recognized researcher and clinician with expertise in racial/ethnic disparities related to provider level factors. Our preliminary work is below.

**Preliminary study 1.** Through this qualitative descriptive study (internal funding), Drs. [name] and [name] identified the most salient needs and challenges of parents of adolescents with DIC. Results indicated that parents' interactions with providers were often aversive, stressful, and nonproductive; suggesting need for an intervention.

**Preliminary study 2.** Similar to the proposed study, we used a 2-phase study to develop and preliminarily test an intervention called FAME (Family Management Efficacy) for parents of adolescents with DIC. With funding (KL2TR001106, UL1TR001108), [name], [name], [name] and a parent and provider advisory board, developed and tested this 6-week parent group-based, in-person intervention among low income African American parents of adolescents with DIC aimed at enhancing parent activation and improving interactions with behavioral health care providers. The setting was the same as for the proposed study. FAME was acceptable but not feasible, and did not show preliminary efficacy on key outcomes because it did not have a provider component. Facilitators noted some parents struggled to develop effective communication skills (e.g., asking questions of providers, sharing ideas about the adolescents' treatments). The team gained valuable experience in intervention delivery to parents of adolescents with DIC and confirmed the importance of simultaneously targeting providers. These lessons inform modification of the evidence-based DECIDE intervention in this proposed study.

**Preliminary work for this application.** Drs. [name], [name], and [name] collaborated with Drs. [name] (40 hours past 3 months) and [name] (10 hours past 3 months), on the following components of this application: identification of target variables for the modified DECIDE, creation of the study conceptual model, selection of study measures, and overall study design.

### **3. Methods**

## DECIDE Parent-Provider Interaction IRB Protocol

**DECIDE Intervention.** The evidence-based DECIDE intervention was developed for low income and/or minority adults with serious mental illness and their providers. DECIDE has both patient and provider components. DECIDE has improved patient activation, patient self-management, perceived quality of care, and improved collaborative treatment decision making. Because DECIDE was designed for individuals who work with adult patients, we will adapt it for parents and providers of adolescents with DIC. For example, case examples need to be relevant to the clinical work with this population and accommodate individual or family therapy; we will also shorten the provider training – to increase feasibility of implementation and acceptability to participants. This fits with Stage 1A and 1B of the ORBIT model.

The **modified DECIDE** will have parent and provider components.

The **parent component** is designed to teach parents how to effectively ask questions and participate in decisions about their adolescents' behavioral health care. It will include up to three 60 minutes sessions (the third session is optional). Session 1 (Decisions and Agency) is designed to increase awareness of their role in clinical interactions and encourage participation and decision making in care. Session 2 (Self-efficacy and Consolidation) encourages parents to ask questions about their adolescents' behavioral health and health care and treatment options . Session 3(Optional Booster), which can discuss any previous topics the parent would like the trainer to review and can also include more practicing of asking questions).

The **provider component** is designed to improve provider communication in three key areas: 1) perspective taking to understand circumstances and perceptions; 2) attributional errors or attributing negative parent behaviors to character traits instead of considering the situational factors; and 3) receptivity to parent participation and collaboration. We will shorten the provider training to increase feasibility of implementation and acceptability to participants. The training will included one 4.5-hour (rather than 12-hour) group workshop.

**Intervention Delivery.** In addition to standard care, all participants will receive the modified DECIDE. Parents receiving intervention will receive up to three 60-minute sessions over the course of three weeks. The sessions will focus on increasing the parent's involvement in decision-making, increasing their understanding of the decision-making process, and training the parents to ask questions concerning their adolescent's care. These training sessions will be delivered by trained study staff virtually via HIPPA compliant video teleconferencing platform (ie Zoom Health) or via Telephone as approved by IRB.

### Phase I, Aim 1

**Recruitment of Parent Advisory Board.** We will form a 5-member parent advisory board to guide modification of DECIDE. Inclusion Criteria. Parents of adolescents with DIC, who are receiving services at Midtown Child and Adolescent Program. We will invite parents sequentially in the clinic as well as parents from our previous study advisory board and who participated in preliminary study 2 that agreed to be contacted for future studies.

**Recruitment of Provider Advisory Board.** We will form a 5-member provider advisory board to guide modification of DECIDE. Inclusion Criteria. Midtown Child and Adolescent Program staffs who do not meet the inclusion criteria in phase II (i.e. manager and clinical coordinators or supervisors). We will invite two other direct care providers who work in the healthcare system but not at recruitment site. No parent or provider will be excluded on basis of race/ethnicity, gender, or sexual orientation.

**DECIDE Modification.** [name] has met both [name] and Midtown Chief Executive Officer, Program manager and clinical coordinators to discuss potential modifications to the provider intervention to increase acceptability and feasibility. We will invite their continued participation during phase I. The research team and provider advisory board will meet monthly for ~ 3 months to modify the intervention. At the initial meeting, the PI will share DECIDE and discuss what components need to be modified. The research team will prepare the modified

## DECIDE Parent-Provider Interaction IRB Protocol

intervention materials and present modifications to the provider advisory group for iterative feedback. The same process will be followed to modify the parent component of the DECIDE intervention. Together, research team and the parents' advisory group will meet twice during the first 4-months of study period. We will (a) share the parent component of the DECIDE intervention, (b) discuss what components need to be modified, (c) have the team do the modifications; and (d) present them back to the parent advisory group for iterative feedback.

### Phase II, Aims 2 and 3.

**Design.** A pilot trial to assess feasibility and estimate outcomes in intervention vs. an historical control.

**Setting.** Similar to preliminary studies, we will conduct this trial at Sandra Eskenazi Mental Health Hospital in Indianapolis, IN, Bowen Center in Indianapolis, IN, Centerstone centers in Indiana, Florida and Tennessee, other applicable mental health centers and private practice in the US. Midtown is the largest publicly funded mental health center in Indiana and serves primarily low income and/or minority population (see Facilities and Resources). Child and Adolescent Program employs 22 masters-prepared mental health providers. [name] also has clinical privileges at Midtown to facilitate recruitment (see support letter). Midtown has named treatment engagement as a top strategic priority.

**Sample.** First, we will recruit 16 providers and then work with them to invite parents (or parent surrogates) of adolescents aged 6 to 17 years who have been diagnosed with a DIC disorder. Ideally, we will enroll 80 parents (5 parents per enrolled provider).

**Sample size justification.** Because this is a feasibility pilot study, statistical models will be fit to estimate effect sizes for use in a future randomized trial. Any inferential testing is considered exploratory though effect sizes of  $\geq 0.65$  could be detected with 80% power in the models described below assuming pre/post exposure correlation of 0.5, intraclass correlation of 5%, and two-tailed test ( $\alpha=0.05$ ). We will follow the recommendation of Hertzog that a minimum of 30 participants per group are needed for pilot studies to examine group comparisons. To account for potential 20% dropout, we will recruit 40 parents to the intervention group with 1-5 parents per provider) for up to a total of 80 parents. Provider sample size is based on availability.

**Procedures.** Enrollment, consent, and baseline data collection. **Providers.** PI will attend provider team meeting at Midtown to introduce the study, answer questions, and invite them to participate. Trained research assistants (RA) will obtain verbal informed consent from interested providers. **Parents.** To screen parents, we will enlist the help of providers and administrative assistants at the clinic, who have access to providers' caseloads, schedules, and adolescent patient demographics. To coordinate recruitment, we will ask the administrative assistants to select adolescents between 6 to 17 years who are diagnosed with DIC. PI and RAs will work determine provider schedules or enrolled parents' next visit. Parent eligibility and consent to participate will be determined by calling parents via telephone or a HIPPA compliant teleconferencing platform (ie Zoom Health). If RA does not make contact with parent, RA will send study flyer and recruitment letter co-signed by PI and Child and Adolescent Program Manager. RA will make follow-up contact within 7 days after the sending the study materials.. If parent express interest in participation, the RA will determine eligibility. Next, RA will obtain verbal consent from interested parents.. Following enrollment, RA will collect baseline data from all providers and parents.. Training for providers will occur as soon after baseline measures are collected.

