If study findings are positive, we will be poised to test the modified DECIDE in a fully-powered R01 level randomized, controlled, multi-site clinical trial. If study findings are negative, we will have process and outcome information needed to further refine DECIDE or pursue different interventions. Either way, this line of research has potential to optimize parent-provider interactions and ultimately, ensure adolescents with DIC receive the behavioral health care they need.

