Modification and evaluation of the DECIDE intervention to improve parent-provider interactions in low-income parents of adolescents with Disruptive Impulse Control, and Conduct Disorders

NCT number: NCT04445155

Date: 12/13/2023

Statistical Analysis Plan for the DECIDE Parent-Provider Intervention Study

The statistical analysis plan was changed from the original statistical analysis plan in the protocol because the study design was changed. Originally, there was a control group planned (treatment as usual); Instead, the study design was changed to a pre/post design, with outcomes collected pre- and post-intervention for three sample populations: 1) Providers; 2) Parents; and 3) a second group of providers (referred to as Provider Substudy).

SAS version 9.4 (Cary, NC) was used for statistical analysis. The alpha level was set at 0.05 for all statistical tests. For each outcome, change scores were calculated as post-intervention score minus pre-intervention score. Next, the change scores were tested for normality using the Shapiro-Wilk test. If the change scores were not normally distributed, then a Wilcoxon signed-rank test was conducted to see if the distribution of the outcome data was different from pre- to post-intervention. If the change scores were normally distributed, then a paired t-test was conducted to test whether the mean difference was not equal to zero. As pre- and post-intervention outcome data was available for only 3 parents, there were no statistical analyses conducted with the parent outcome data; thus, statistical tests were only generated for the Provider and Provider Subgroup outcomes.

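### The protocol promises effect sizes for a future randomised trial, but the SAP's one-group pre/post change is not a between-group effect and, at the planned numbers, is too imprecise to size one

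*Protocol*

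**What the plan says.** The protocol's sample size justification (Section 6.0, Phase II, Aims 2 and 3) says that "statistical models will be fit to estimate effect sizes for use in a future randomized trial". It calls testing exploratory, but adds that effects of 0.65 or more "could be detected with 80% power in the models described below", "assuming pre/post exposure correlation of 0.5, intraclass correlation of 5%, and two-tailed test" at a two-sided 0.05 level. Section 3.0 describes what follows positive findings: "we will be poised to test the modified DECIDE in a fully-powered R01 level randomized, controlled, multi-site clinical trial".

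The documents describe the comparison in three ways that do not agree:

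- Section 3.0 still describes a randomised two-group pilot against usual care.
- Section 5.0 (Randomization) puts everyone in the intervention arm and compares results with historical data. The design statement, study schema, Aim 3 measures and fidelity text in Section 6.0 repeat the historical comparison. None gives that group's source, size or measures. Section 9.0 keeps a mixed model with a treatment-versus-usual-care term, T1 as covariate, and omega-squared as the effect size.
- The SAP says: "Instead, the study design was changed to a pre/post design". It tests change scores by paired t-test or Wilcoxon signed-rank test. It mentions no historical group and names no effect-size estimate or interval. It reports paired data for only 3 parents, so parent outcomes were not analysed.

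**The concern.** The planning sentence and the power statement belong to a two-group comparison and were not revised when the control arm went. Under the SAP, the only quantity available is change within people who all received the intervention on top of standard care. That change includes re-test effects, regression to the mean, expectation and whatever ordinary care would have produced. A randomised trial subtracts these from its treatment effect; a one-group change keeps them. The planned numbers also make the estimate imprecise, and provider numbers rest on availability rather than on a precision target.

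At stake is the planning of the next trial. A sample size built on this change could be far too small or far too large, and nothing in the documents warns against using it that way.

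**Working it through.** **Inputs.** Correlation 0.5, ICC 0.05, 80% power and two-sided 0.05 are from the sample size justification; the SAP agrees on the level ("The alpha level was set at 0.05 for all statistical tests"). On parents: "To account for potential 20% dropout, we will recruit 40 parents to the intervention group with 1-5 parents per provider) for up to a total" (given as 80), so 40 × 0.8 = 32 evaluable. Elsewhere in the same section: "Ideally, we will enroll 80 parents (5 parents per enrolled provider"), which gives 64 evaluable, and 5 × 0.8 = 4 evaluable parents per provider. Providers: 16 planned. The SAP gives no provider number.

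**1. Reproduce the 0.65.** Two-group covariance analysis, normal approximation:

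- Design effect = 1 + (4 − 1) × 0.05 = 1.15
- Detectable effect = (1.960 + 0.842) × √[2 × 1.15 × (1 − 0.5²) / 32] = 2.802 × 0.232 = 0.650
- Power at 0.65 is 79.9% (78.7% with the t distribution)

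The figure is right for 32 per group with a concurrent comparison group, which the study no longer has. Even that design gives a 95% half-width of 1.96 × 0.232 = 0.455, about 0.46 SD.

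**2. Precision of a one-group change.** In units of the score SD, the SD of change is √[2(1 − r)] = 1 at r = 0.5. Half-width = t × √[2(1 − r) × DE / n], where DE is the design effect.

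| Sample | DE | 95% half-width (SD) |
|---|---|---|
| 16 providers | 1 | 2.131 × 0.250 = 0.53 |
| 32 parents | 1 to 1.15 | 2.040 × 0.177 to 0.190 = 0.36 to 0.39 |
| 64 parents | 1.15 | 0.27 |
| 3 parents (SAP) | 1 | 4.303 × 0.577 = 2.48 |

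For r from 0.7 to 0.3 the provider figure runs from 0.41 to 0.63. The normal-approximation detectable change at 80% power in 16 providers is 2.802 × 0.250 = 0.70 SD. So 0.65 does not carry over to that analysis.

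**3. What that width means for sizing.** For a 1:1 trial without clustering or covariate gain, n per arm = 2 × 2.802² / d² = 15.7 / d². Suppose 16 providers show a change of 0.65, with interval 0.12 to 1.18. The size per arm is 38 at the estimate, about 1,145 at the lower limit and 12 at the upper limit.

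**4. Chance that the next trial is undersized.** Suppose it is sized for 80% power on the point estimate. Its true power is below 80% when the estimate exceeds the true between-group effect. If the estimate is normal around (true effect + b), where b is the non-specific shared change, that probability is Φ(b / SE), whatever the true effect. SE is √(1/16) = 0.250 for providers and √(1.05/32) to √(1.15/32) = 0.181 to 0.190 for parents.

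| b (assumed, SD) | 16 providers | 32 parents |
|---|---|---|
| −0.1 | 34% | 29 to 30% |
| 0 | 50% | 50% |
| +0.1 | 66% | 70 to 71% |
| +0.2 | 79% | 85 to 87% |
| +0.3 | 88% | 94 to 95% |

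Going ahead only after an estimate above zero raises these figures a little when the true effect is small. With 16 providers, true effect 0.30 and b = 0, the chance is 0.50 / Φ(0.30/0.25) = 0.50 / 0.885 = 57%.

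**5. Size of the shortfall.** Take b = 0.2 and the pilot's expected value. For true effects of 0.30, 0.50 and 0.65, the planned size per arm is 63, 33 and 22 against 175, 63 and 38 needed. True power is 39%, 53% and 58%.

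**The case against.** **The protocol does not describe a pure one-group change.** It names a historical comparator and a group term in the model. A historical group measured twice would remove some of the shared change. This stands as a correction to any reading that takes the protocol's own estimate to be pre/post change; that description comes from the SAP alone. It does not rescue the estimate, because the historical group is undescribed and non-randomised, and the SAP leaves it out.

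**No document says that the one-group change will be the planning difference.** The intended use is stated in the protocol, next to a comparative model. The SAP mentions no future trial. A lower limit, a discounted estimate or pooling with other evidence would fit the wording equally well. This stands, so the probabilities above are conditional on undiscounted use.

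**A reader might infer that the next trial would probably be underpowered.** The documents do not support that. With no shared change the chance is about 50%, which is just the symmetry of an unbiased estimate, and with unfavourable shared change it falls to about 29 to 34%. It becomes probable only with favourable shared change or selection on success. Section 3.0 hints at selection by tying the larger trial to positive findings, but does not define positive. If it meant a significant change, 16 providers would have to show more than 0.53 SD. Any true effect below that would then be undersized even with b = 0.

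**A reader might also infer that the pilot fails in its main purpose.** Aim 2 is feasibility and acceptability, which this point does not touch.

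**The pilot's other planning inputs are imprecise too.** With 16 providers, the 95% interval for an SD is 0.74 to 1.55 times the estimate, a (1.55/0.74)² = 4.4-fold spread in sample size. A correlation of 0.5 has an interval of about 0.01 to 0.80. This is true, and the fix has to say so. These inputs do not, however, present within-group change as an effect against usual care.

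**Conclusion.** The concern holds in a limited form. The protocol's stated use of its effect sizes, and its 0.65 detectable effect, rest on a two-group comparison that the SAP's analysis does not provide. What remains is a provider pre/post change with a 95% half-width of about 0.53 SD, if the planned 16 providers are all measured twice and the correlation is 0.5. No usable parent effect size exists with 3 pairs. Reaching 32 parents would have given 0.36 to 0.39 SD. More parents would have narrowed the interval without removing the non-specific change.

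The consequence for the next trial depends on a choice that the documents leave open. With undiscounted use of the point estimate, the chance of true power below 80% is about 50% from imprecision alone, and about 65 to 95% with 0.1 to 0.3 SD of favourable shared change. The size and direction of that shared change, the true effects of 0.30 to 0.65 used for the shortfall, and the simple 1:1 design are assumptions, not figures from the documents.

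**What to change.** - Reconcile the sample size justification and Section 9.0 of the protocol with the SAP. Either describe the historical group (source, size, measures, timing) and how it enters the analysis, or remove it together with the treatment-group term.
- Remove the 0.65 and 80% power statement, or restate it for the one-group analysis with its sample size.
- Report provider pre/post change with a 95% confidence interval, labelled as within-group change and not as an effect against usual care. State that no parent effect size is available.
- State that the observed change will not be the planning difference. Size the next trial on a stated minimum worthwhile between-group difference. Take enrolment and completion rates, outcome SD and T1–T2 correlation from the pilot with their confidence intervals, and acknowledge that these are also imprecise at 16 providers.

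The cost is wording and one interval per outcome. The SAP is written in the past tense, so the changes matter mainly for the study report and the next application. The real burden is that the team must justify a minimum worthwhile difference.

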### **Randomization**

All participants will be assigned to the intervention arm and there will be no randomization. Instead, the intervention results will be compared to historical data.

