#### Revised Study Schema:

Figure 2: Study Schema							
Providers	Recruitment	Screening	Consent	Baseline	Modified DECIDE intervention [workshop ([contact] hrs)]	Time 2	DECIDE Oral Interview (all providers)

**DECIDE Parent-Provider Interaction  
IRB Protocol**

Parents	Recruitment	Screening	Consent	Baseline	Modified DECIDE sessions 2 @ 1 hr/week, with an optional 3 rd booster session offered @ 1 hr/week	Time 2	DECIDE Oral Interview (subset of parents)
Green: Quantitative measures and oral interviews							
All participants will receive the DECIDE intervention. Results will be compared to historical control.							

Training for parents will be delivered remotely using telephone and/or Zoom Health for parents with video capability. The parents will be sent a Zoom Health invitation which include a toll free number they can call. This allows research staff to record sessions for fidelity checks.

**Data collection.** A trained study staff will collect baseline data (T1) before the provider takes the DECIDE Training and will schedule a follow-up assessment 1- 4 weeks post intervention training (T2). Providers will be instructed to think specifically about the most recent therapy session that he/she had with a parent of a child diagnosed with DIC in order to keep the parent provider interaction fresh in the provider's mind when completing the measures. Study staff will follow these same guidelines for scheduling the T2 data collection. Providers will complete and enter their surveys directly into REDCap. Providers will be contacted by study staff to remind them to complete their surveys and to answer any questions if necessary. Study staff will schedule an appointment with providers to collect the post-intervention (T2) measures in order to ensure the provider understands the instructions and also to conduct the post-intervention qualitative interview. Providers will be instructed to think specifically about the most recent therapy session that he/she had with a parent of a child diagnosed with DIC in order to keep the parent provider interaction fresh in the provider's mind when completing the measures. Parents will be contacted and asked to schedule a convenient time to complete the surveys with the study staff.

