### **9.0 Statistical Considerations**

We will calculate the proportion eligible that enroll and proportion completing the intervention for both parents and providers. We will tabulate responses to Parent and Provider Satisfaction with Intervention items and calculate the proportion of parents and providers who have a mean ratings of at least 4 on the 5-point scale (satisfied or highly satisfied). Effect sizes will be estimated by fitting linear mixed models, with parent, provider, or observer target and outcomes variables, all measured at T2, as outcomes and treatment group (intervention or usual care) as the explanatory variable. All models will also include the T1 outcome as a covariate and random effects for provider and parent nested within provider to account for clustering. Effects sizes will be estimated with  $\omega^2$ . Analyses will be intent-to-treat and conducted using SAS Version 9.4 (SAS Institute Inc., Cary, N.C., Copyright 2002-2012).

*Supplementary Analyses:* We will investigate how the adjustment for covariates (age of child, sex of provider and parent, parent race and income, severity of child illness and duration in treatment) impacts effect size estimates by adding interaction terms to models and estimating effect sizes separately for different levels of the covariate (e.g. male and female for parent gender). *Missing Data:* We will compare baseline variables between subjects who drop out of the study to those who do not using two-sample *t* tests, chi-square tests or their non-parametric equivalents as appropriate. If we find that the missing data appear to be MNAR, this information will be used in designing the larger trial. Because of the relatively small sample size, we will not attempt to model the missing data mechanism in this pilot study. *Sex as a biological variable:* As noted above, we will estimate effect sizes by sex for all outcomes. [name] will lead the qualitative analysis of the semi-structured interviews with input from PI and research team. The interviews will be coded with standard content analytic procedures.

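### The only power figure (80% for effects of 0.65 or more) belongs to a superseded two-group parent comparison; it was not attained for parents and is not shown for the paired provider tests in the SAP

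*Protocol*

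**What the plan says.** Protocol 6.0, under Sample size justification, contains the only power statement in either document. Effects of at least 0.65 "could be detected with 80% power in the models described below assuming pre/post exposure correlation of 0.5, intraclass correlation of 5" per cent, with a two-sided alpha of 0.05. The same paragraph calls testing exploratory, gives the purpose as estimating effect sizes for a later randomized trial, plans 40 intervention parents to allow for 20% dropout, and lets availability set the number of providers. The recruitment target under Sample is 16 providers.

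The models referred to are in Protocol 9.0. They take "parent, provider, or observer target and outcomes variables, all measured at T2, as outcomes and treatment group (intervention or usual care" as the explanatory variable, with the T1 value as a covariate and random effects for provider and for parent within provider.

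Elsewhere the protocol has already given up the concurrent control. Under Randomization in 5.0: "Instead, the intervention results will be compared to historical data". Under Design in 6.0, the aim is to "estimate outcomes in intervention vs. an historical control", and the Revised Study Schema says "Results will be compared to historical control". Intervention Fidelity in 6.0 repeats the comparison. None of these places gives the size of the historical control.

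The SAP says: "Originally, there was a control group planned (treatment as usual); Instead, the study design was changed to a pre/post design". If change scores look normal, "a paired t-test was conducted to test whether the mean difference was not equal to zero"; otherwise a Wilcoxon signed-rank test is used. Paired data existed for only 3 parents, so "statistical tests were only generated for the Provider and Provider Subgroup outcomes". The SAP gives no size for either provider sample.

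**The concern.** The power figure and the analysis differ in three respects: the model (baseline-adjusted two-group against paired change), the comparator (usual care against none) and the population tested (parents against providers). The SAP discloses the design change, but neither document says that the 0.65 and 80% figures do not carry over.

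What is at stake is how the pilot's results are read when the next trial is planned. Someone who sees a non-significant provider result beside the protocol's 80% could take it as evidence against an effect of 0.65, and nothing in the documents shows that the provider tests had that sensitivity. The SAP adds to the risk. The pilot is meant to estimate effect sizes, yet the SAP specifies only tests against zero, with no intervals to show how precise the estimates are.

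**Working it through.** **1. Reproduce the protocol's figure.** I read 0.65 as a difference in SD units, since the protocol gives no unit. Inputs from the sample size justification: r = 0.5, ICC = 0.05, two-sided alpha 0.05, power 80%, 40 parents less 20% = 32 completers. Inferred: 32 in each group, and 5 parents per provider less 20% = 4.

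- Baseline adjustment leaves a variance factor of 1 − 0.5² = 0.75.
- Design effect: 1 + (4 − 1) × 0.05 = 1.15.
- Detectable effect = (1.960 + 0.842) × √[0.75 × 1.15 × (1/32 + 1/32)] = 0.650.

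The figure is therefore sound for the model it names. The group sizes are an inference: 40 versus 27 gives 0.648 and 64 versus 22 gives 0.643. With 5 completers per provider (design effect 1.20), 32 versus 32 gives 0.664.

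**2. Parents as the SAP reports them.** With 3 parents, and even with an assumed 1,000 historical controls, the same formula gives 2.802 × √[0.75 × 1.15 × (1/3 + 1/1000)] = 1.50 SD. This keeps the design effect of 1.15; without it, the result is 1.40 SD. The number of parents is the limit, so stating a control size could not restore 0.65.

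**3. Providers under the paired t-test.** The number of pairs and the provider pre/post correlation are not in the documents, so this is an illustration only. The SD of change is √[2(1 − r)] times the outcome SD, which equals 1 SD at r = 0.5. Power is from the noncentral t distribution with n − 1 degrees of freedom and noncentrality (0.65 / SD of change) × √n. The 95% CI half-width is t(0.975, n − 1) × SD of change / √n.

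| Pairs | r | Power at 0.65 | Effect at 80% power (SD) | CI half-width (SD) |
|---|---|---|---|---|
| 13 | 0.5 | 58% | 0.85 | 0.60 |
| 16 | 0.3 | 54% | 0.89 | 0.63 |
| 16 | 0.5 | 68% | 0.75 | 0.53 |
| 16 | 0.7 | 88% | 0.58 | 0.41 |
| 20 | 0.5 | 79% | 0.66 | 0.47 |
| 21 | 0.5 | 81% | 0.64 | 0.46 |
| 24 | 0.5 | 86% | 0.60 | 0.42 |

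The smallest number of pairs with at least 80% power at 0.65 is 28 for r = 0.3, 21 for r = 0.5, 17 for r = 0.6 and 14 for r = 0.7. By simulation with normal changes and r = 0.5, the signed-rank test has about 64% power with 16 pairs and reaches 80% at 22.

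**4. A caution on method.** Step 1 uses normal quantiles and step 3 the noncentral t. On the noncentral t, 32 versus 32 has 78.7% power, the same as 20 pairs at r = 0.5. Small differences around 20 or 21 pairs therefore mean little.

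**The case against.** The strongest reply is that the figure already limits itself. It refers to named models with an ICC, testing is labelled exploratory, the provider number is openly a matter of availability, and the SAP begins by saying that the design changed. A careful reader of both documents would not apply the 80% to the provider tests. In addition, the SAP is written in the past tense, so rewording a prospective power sentence alters no result. All of this stands, and it keeps the point out of the serious class. It does not remove the point: the one sensitivity figure on record is left in place beside analyses to which it does not belong. The interval estimates would be worth having even if the protocol made no power statement, because estimation is the pilot's declared purpose.

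Four stronger readings are tempting, and the documents do not support them.

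- A reader might infer that the provider tests are underpowered. Neither the number of pairs nor the correlation is given, and at 16 pairs power at 0.65 lies on either side of 80% depending on r.
- A reader might infer that 0.65 is a miscalculation. It reproduces.
- A reader might infer that giving the historical-control size would settle the matter. With 3 parents it would not.
- A reader might apply the Protocol 9.0 model to providers and compute a two-group deficit. That needs an assumption of one record per provider and no clustering, whereas the model nests parents within providers.

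**Conclusion.** The point holds as a mismatch between the power statement and the analysis performed. The 0.65 and 80% figures describe a clustered, baseline-adjusted comparison of two parent-sized groups. That comparison was superseded, the sensitivity was not attained for parents (3 with paired data), and it is neither shown nor refuted for providers. The historical comparison named in four places in the protocol has no counterpart in the SAP.

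The weight is minor to moderate. The validity of the trial is not affected, and no decision rule depends on the 80%. The conclusion about which model the figure describes rests on the text itself. The group sizes behind it are inferred, and the provider figures assume 13 to 28 pairs and correlations of 0.3 to 0.7.

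**What to change.** No further enrolment is needed.

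1. In the protocol's sample size justification, state that the 0.65 and 80% figures applied only to the superseded two-group parent comparison, do not carry over to the paired provider tests, and were not attained for parents (3 pairs). Reconcile the historical comparison in Protocol 5.0 (Randomization) and 6.0 (Design, Revised Study Schema, Intervention Fidelity) with the SAP by stating that it is withdrawn.
2. In the SAP, report each Provider and Provider Substudy change as an estimate with a 95% confidence interval and the number of pairs: the mean change where the paired t-test is used, and the Hodges-Lehmann shift where the signed-rank test is used. If a sensitivity figure is quoted, label it as design-based and give the assumed number of pairs and correlation.

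The cost is a few sentences and a little extra analysis of data already collected. The intervals may be wide, and readers planning the next trial need to see that.
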